Note: *For easy reference by the participating practitioners and patients, this study will be referred to as the Sensitive Teeth Study on most of the practitioner and patient study documents and communications.*

Précis: This is a prospective, multicenter cohort study of patients with dentin hypersensitivity. For the study, practitioners and patients will be recruited from six National Dental PBRN regions across the US. The study population will consist of adult dental patients (19 years old or older) who have dentin hypersensitivity and the practitioners who provide treatment for this condition. It is anticipated that approximately 180 dentist practitioners across the US will be enrolled (30 practitioners per National Dental PBRN region). Each dental practitioner will be asked to enroll approximately 14 study patients, with an enrollment aim of 2,520 adult patients for the entire network.

Objectives: **The primary objective** of the study is to gain a better understanding of the multiple treatments used to manage dentin hypersensitivity among US dental practitioners by: characterizing methods of diagnosing dentin hypersensitivity in the practice setting, characterizing dentists' selected treatment(s) of dentin hypersensitivity, and characterizing patient-reported pain outcomes over time.

The secondary objectives of the study are to explore patient-, practitioner-, practice- and tooth- level characteristics that may contribute to practitioners' selected treatment(s) and approach(es) to care, and to characterize patients' satisfaction with the received treatment of dentin hypersensitivity.

[figure not shown]
Primary Outcomes: Data will be gathered on diagnostic methods and treatment modalities that are used for diagnosis and management of dentin hypersensitivity in the practice setting. Patient-reported pain outcomes will be assessed by a reduction in dentin hypersensitivity based on patients' perception of pain assessed by the Visual Analog Scales (VAS) at baseline and at 1 week, 4 weeks and 8 weeks post baseline. Duration, intensity, tolerability and pain description changes will be

assessed by means of the Labeled Magnitude (LM) scales at baseline and at 1 week, 4 weeks and 8 weeks post baseline.

Secondary Outcomes: Several patient-, practitioner-, practice- and tooth level characteristics will be collected to explore their relevance to practitioners' selected treatment(s) and approach(es) to care.

- Population:** The proposed study will include as subjects approximately 180 dentists and approximately 2,520 adult patients (19 years old or older) from the National Dental PBRN. Patients will represent demographic groups in proportion to the practice population.
- Number of Sites:** Approximately 180 National Dental PBRN practices
- Study Duration:** 24 months
- Patient Participation Duration:** Between 8-24 weeks
- Estimated Time to Complete Enrollment:** Approximately 2-4 months for practitioners; 4-6 months overall

Schematic of Study Design:

2 INTRODUCTION: BACKGROUND INFORMATION AND SCIENTIFIC RATIONALE

2.1 Background Information

Dentin hypersensitivity (DH) has been defined as a “short, sharp pain arising from exposed dentin in response to stimuli typically thermal, evaporative, tactile, osmotic or chemical and that cannot be ascribed to any other form of dental defect or pathology”(Canadian Adv, 2003). The stimulus that may trigger the onset of pain can be characterized as being of thermal, chemical or mechanical origin. One of the most frequent patient complaints is related to cold stimuli; pain may also occur when consuming acidic foods (mainly fruit), sweets and salty foods. Mechanical stimulus frequently occurs when the patient brushes his/her teeth or rubs the sensitive area with a finger nail (Porto et al., 2009).

DH is considered to be a relatively common problem encountered in clinical practice. It may disturb patients during eating, drinking and brushing. The prevalence of DH has been reported to be in the range of 8 to 57% in the general population (Amarasena et al., 2010, 2011; Canadian Adv, 2003; Chu et al., 2011; Cummins, 2011; Parolia et al., 2011; Poulsen, 2006; Liu et al., 1998; Gillam et al., 1999; Cunha-Cruz et al., 2013). The diversity of reports could be in part due to different methods used to diagnose this condition and also relying solely on questionnaire data (Dababneh et al., 1999).

For example, among 780 patients that presented to the Health Examination Center of National Taiwan University Hospital, the prevalence of DH was 32% (Liu et al., 1998). The self-reported prevalence of DH among regular attenders in three general dental practices in the United Kingdom was 52%; DH was most prevalent among 30-40 year old patients and it was more common among female patients (Gillam et al., 1999). A cross-sectional study conducted by 19 dental practitioners in the United Kingdom that examined 4,841 patients over a period of one calendar month revealed that 4.1% of patients were diagnosed with DH based on the dentist examination. Upper premolars were the most commonly affected, and cold drinks initiated DH most often. A greater number of sensitive teeth were found in patients with periodontal disease who also smoked (Rees & Addy, 2002).

Data on diagnostic methods used, treatments employed, and perceived success of the treatments were collected in a web survey (December 2008 to June 2009) of Northwest PRECEDENT dentists (n=209; 177 generalists, 32 specialists). Based on the survey, practitioners used a diverse range of methods to identify and characterize DH. The most frequently reported diagnostic method was a spontaneous patient report. Patient reports prompted by a query from the dentist were also common but used less frequently. Practitioners frequently requested a verbal or numeric pain description or asked the patient to rate their pain on a Visual Analog Scale (VAS). The use of a dental explorer or air blast was the most common method of assessing DH clinically (Cuhna-Cruz et al., 2010).c

No clear consensus among Northwest PRECEDENT dentists existed for successfully treating DH, but fluoride varnishes and gels apparently had the most support. Dentists also expressed high levels of interest in testing fluoride varnishes and gels, as well as glutaraldehyde/HEMA and restorative treatments in future studies (Cunha-Cruz et al., 2010).

DH affects patients of any age with its peak occurrence in middle aged adults. It may affect any tooth, but most often affects canines and first premolars because they are prominent in the arch. It may present clinically on any tooth surface, but most often it occurs on the buccal cervical margins of teeth. Several theories of DH have been proposed. These include hydrodynamic theory, odontoblast transduced mechanism and direct innervation theory (Parolia et al., 2011). None of these mechanisms fully explain this phenomenon. There are a multitude of products that are available for treatment of DH with no conclusive evidence present of reliable and successful treatment regimens, especially in the practice environment.

Based on a cross-sectional survey of 787 adult patients from 37 general dental practices within the Northwest PRECEDENT PBRN that was conducted from September 2010 to May 2011, prevalence of DH was 12.3% (Cunha-Cruz et al., 2013). Patients with hypersensitivity had, on average, 3.5 hypersensitive teeth. The prevalence of DH was higher among patients who were 18-44 years of age and lower among patients who were 65 years of age or older. The prevalence of DH was higher among women and patients with gingival recession and patients who used at home tooth whitening products (Cunha-Cruz et al., 2013).

Although dentin sensitivity appears to be prevalent in adult population groups, no universally used or highly reliable desensitizing agents or treatment modalities have been identified (Holland et al., 1997; Orchardson & Gillam, 2006). Recently the PEARL PBRN conducted a randomized clinical trial, in the practice setting, to assess the outcomes of noncarious cervical lesion treatment choices (Veitz-Keenan et al., 2013). The overall objective of this study was to determine the efficacy of three randomly assigned treatments for hypersensitive noncarious lesions: chemoactive dentifrice use, dentin bonding agent with sealing and flowable resin-based composite restoration. The secondary outcomes were to assess tubule occlusion, retention of resin coating, retention of restoration and change in lesion size. Results of this study suggest that placement of the sealant or resin restoration was effective in reducing hypersensitive noncarious cervical lesions over the six-month study period.

According to the survey of dental practitioners conducted by the Canadian Advisory Board on Dentin Hypersensitivity, approximately 50% of the respondents reported lack of confidence in managing patients' pain due to DH (Canadian Adv, 2003). As suggested by the Canadian Advisory Board on Dentin Hypersensitivity, providers should initiate management of this condition by applying desensitizing treatment that is noninvasive; i.e., desensitizing toothpaste and/or topical agents. Some dental providers use a stepped approach to treatment with multiple visits; others apply and prescribe

multiple treatments at one time. Invasive treatments of DH are also performed by placing a restoration on an otherwise healthy tooth (Canadian Adv, 2003).

2.2 Rationale

The proposed study, which will take place in dental offices across the country that are part of the National Dental PBRN, is optimally located as it brings “real world” settings to the treatment of DH. In this environment, little is known about the products and methods dentists use to treat DH, nor is much known about the effectiveness of these products and treatment modalities. There are various treatment options available to manage DH including conservative and invasive approaches and little is known about their effectiveness.

Given that no universally-accepted guidelines are available to treat DH; this could be the first national study to address this question in the office practice setting. Several techniques have been used to diagnose, treat and manage DH in the practice setting. The ideal desensitizing modality should not irritate the pulp, and should be relatively painless when applied or shortly thereafter, easily applied, fast acting, permanent, and cost effective, and it should not discolor the tooth. A plethora of treatment modalities used for treating DH by dental clinicians suggest that there is no single treatment that may meet the ideal criteria and there is no gold standard for treating DH. Some dental providers use a stepped approach to treatment with multiple visits; others apply and prescribe multiple treatments in a single visit.

By conducting a prospective cohort study, rather than a randomized controlled trial, we can build a picture of how patients with DH are cared for in dental offices in the US and how the practitioner, practice, patient and tooth characteristics relate to the approach to care to provide data for practice guidelines in this domain. This approach has been used effectively in other clinical studies. For example, in a prospective cohort study that evaluated treatment modalities for febrile infants, clinicians did not follow the existing guidelines and used individualized clinical judgment resulting in fewer hospitalizations and unnecessary laboratory testing (Pantell et al., 2004). The proposed study, utilizing data from a sample of National Dental PBRN enrolled dental providers, will improve our knowledge about treatment methods and products that are effective when treating DH and may eventually lead to the establishment of evidence-based guidelines for treating DH.

2.3 Potential Risks and Benefits

This is an observational study. The participants of the study will not receive dental care as a study procedure, but will continue to receive the usual clinical care as patients of the dentists participating in the study. Risks of dental procedures provided as part of usual clinical care are not considered to be study-associated.

2.3.1 Potential Risks

As with any study, there is the possibility of breach of confidentiality. Appropriate precautions will be taken and procedures will be followed to maintain confidentiality of subject information and data. These include use of unique study codes for participants, encryption of data for transmission to the coordinating center, and password-protected computers for data storage. Compliance with all Institutional Review Board (IRB) regulations concerning data collection, data analysis, data storage, and data destruction will be strictly observed.

2.3.2 Potential Benefits

Participation in the study will provide no direct benefit to study participants. Benefits will accrue to society related to better understanding of treatment options of DH and the patient-reported pain outcomes over time. Participation in the study may enhance care for future patients through evidence-based recommendations for more timely and appropriate interventions.

3 OBJECTIVES

3.1 Study Objectives

3.1.1 Primary Objective

The primary objective of the study is to gain a better understanding of the multiple treatments used to manage DH among US dental practitioners by:

- Characterizing methods of diagnosing DH in the practice setting,
- Characterizing practitioners' selected treatment(s) of DH, and
- Characterizing patient-reported pain outcomes over time.

3.1.2 Secondary Objectives

The secondary objectives of the study are to:

- Explore patient-, practitioner-, practice- and tooth- level characteristics that may contribute to practitioners' selected treatment(s) and approach(es) to care, and
- Characterize patients' satisfaction with the received treatment of DH.

3.2 Study Outcome Measures

3.2.1 Primary Outcomes

To characterize diagnosis and treatment of DH in the practice setting, practitioners' preferred methods of diagnosing and treating DH will be ascertained via a practitioner

online questionnaire to be completed upon study enrollment and via practitioner data collection forms during patient visits.

Diagnosis of dentin hypersensitivity:

Online practitioner questionnaire: Practitioners' preferred diagnostic procedures that are usually implemented when diagnosing DH in the practice setting will be ascertained. These will include: spontaneous patient report, patient report after dentist's query, applying air blast, applying cold water, scratching dentin with dental explorer, requesting numeric descriptor of pain, requesting visual scale descriptor of pain, and using an electric pulp tester.

Treatment modalities:

Online practitioner questionnaire: Practitioners' preferred method of treatment of DH and the rationale for the elected treatment or treatments will be ascertained. Questions will include preferred treatment modalities (see below) and approach(es) to treatment of DH (i.e., providing multiple treatments at one time, one treatment or staged approach, no treatment, and/or no advice).

Patient visit(s): The usual and customary treatment(s) for DH utilized by the participating practitioner will be applied or prescribed and recorded.

The following groups of treatment modalities will be ascertained:

1. Fluoride products (gels, varnishes, pastes, rinses)
2. Desensitizing over the counter (OTC) Potassium nitrate toothpastes
3. Glutaraldehyde/HEMA products
4. Bonding agents
5. Sealants
6. Restorative treatments
7. Lasers
8. Oxalates
9. No treatment
10. Advice
11. Other

Patient-reported pain outcomes:

Patient visit(s) and follow-up: Patient-reported pain outcomes will be assessed by changes in patient report of pain intensity, duration, and frequency. Patients' perception of pain will be assessed by the Visual Analog Scale (VAS) at baseline, 1 week-, 4 weeks- and 8 weeks- post-baseline. Duration, intensity, tolerability and pain description changes will be assessed by means of the Labeled Magnitude (LM) scales at baseline, 1 week-, 4 weeks- and 8 weeks- post-baseline (Heaton et al., 2013). If patients return

for a second- or third-line of treatment, these pain assessments will be implemented also at 1, 4 and 8 weeks after the initiation of the second- or third-line of treatment.

To the extent possible with the data, pain outcomes will be characterized by patient's predisposing variables that may affect pain reporting, such as age, gender, race/ethnicity, and education level.

3.2.2 Secondary Outcomes

The proposed study will be conducted in six regions of the National Dental PBRN, allowing for a comparison among regions in relation to practitioners' approach(es) to care and treatment of DH based on the patient-, practitioner-, practice- and tooth- level characteristics. To explore the association between the above level characteristics and approach(es) to treatment for DH listed above, several patient-, practitioner-, practice- and tooth- level characteristics will be collected at baseline.

Patient characteristics:

Because this objective will explore characteristics that may contribute to practitioners' selected treatment(s) and approach(es) to care, the practitioner will be asked about the following patient variables at/or soon after the baseline visit:

Patient's predisposing variables: prior periodontal surgery and/or scaling and root planing, recent bleaching history, previous DH episodes and previous/current treatment modalities if any.

Patient's enabling variables: out-of-pocket cost for treatment and/or follow-up appointments after considering dental insurance coverage.

Practitioner characteristics:

The following practitioner variables will be collected upon enrolling in the National Dental PBRN by means of the enrollment questionnaire: age, gender, race/ethnicity, and year of graduation from dental school.

Knowledge about the etiology of DH and predisposing factors related to DH will be ascertained in the practitioner online questionnaire at study enrollment.

Practice characteristics:

The following practice variables will be collected from the practitioner as he/she enrolls in the National Dental PBRN by means of the enrollment questionnaire: practice size, location, practice business, wait time for new patients to be seen, number of patient visits per week, and hours of patient care per week.

Tooth (teeth) characteristics:

The following patient sensitive tooth (teeth) variables will be collected at the baseline visit: number of teeth that are sensitive, tooth (teeth) location, gingival recession, exposed dentin, recent periodontal surgery relating to the sensitive tooth (teeth), number of remaining teeth (surrogate for oral/dental functioning), whether or not the sensitive tooth has a restoration and, if so, the type of restoration, and location and number of surfaces restored.

Patient Satisfaction:

To assess patients' satisfaction with the received treatment for DH, patients' satisfaction with the prescribed treatment modality will be assessed via VAS at 8 weeks post-baseline and will be compared with the treatment rendered. For patients who return for a second- or third-line of treatment, the VAS assessment will be implemented at 8 weeks after the initiation of the last line of treatment.

At each assessment (1-, 4-, and 8- weeks post-baseline), patients will be asked whether or not they complied with the practitioners' treatment recommendation(s).

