- Study patients will complete baseline assessments in dental offices and then will complete follow-up assessments 1-, 4- and 8-weeks post-baseline visit via an online or mailed questionnaire to record patient-reported pain outcomes. Patients who do not have a reduction of symptoms after the first-line treatment may return to the participating dentist due to continued discomfort and/or dentists' recommendation for a second-line treatment. If this occurs within 8 weeks of the initial treatment, study procedures (VAS, LM scales, and clinical exam) will be repeated for the second-line treatment administered or prescribed. The same process will apply if a third-line treatment is administered or prescribed. For patients who receive second- or third- line treatment, follow-up assessments will be obtained via online or mailed questionnaire at 1-, 4- and 8- weeks after the initiation of the second- or third-line of treatment, and follow-up assessments from the previously administered or prescribed treatment will no longer be warranted. Patients will be followed until approximately 8 weeks after the last administered treatment of DH, if it occurs within 8 weeks of the initial treatment. Patients' participation in the study will be 8 to 24 weeks as presented in the study flow diagram (page xi).
- It is anticipated that each practitioner will be able to enroll approximately 14 patients in 2-4 months. It is expected that the study will be fully-enrolled in approximately 6 months.
- The study duration for patients will be at minimum 8 weeks, to include in-office treatment for DH followed by follow-up assessments via online or mailed questionnaire at 1-, 4- and 8- weeks after treatment. Patients who return for second- or third-line treatments during the initial 8-week period due to pain and/or dentist's recommendation will be followed through 8 weeks after the last administered and/or prescribed treatment (maximum study length for patients is approximately 24 weeks).

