6.5 Final Follow-up Assessment

Final Follow-up Assessment 3, Day 56 (-6 days to +6 days) (t_{1_3})

Patients will complete pain assessment/compliance/satisfaction with treatment questionnaire.

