6.6 Study Visits for Patients Returning for Additional Treatment

- Patients who do not have a reduction of symptoms after the first-line treatment may return to the participating dentist for a second-line treatment due to continued discomfort and/or dentist's recommendation if the dentist routinely utilizes a "stepped approach" to DH management. If this occurs within 8 weeks of the initial treatment, study procedures (VAS, pain intensity, clinical exam) will be repeated for each second-line and third-line treatment that is administered or prescribed.
- Recommended (by dentist) and actual (when appointment occurs) time interval(s) between treatment(s) will also be recorded. Patients will be contacted via text message system, phone or email 1-, 4- and 8-weeks post-additional treatment and will be followed until 8 weeks after the last administered DH treatment.

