7.2 Questionnaire Administration

Prior to enrolling study patients, participating practitioners will complete an online practitioner questionnaire that will ascertain modalities used to diagnose DH as well as treatment modalities and approaches towards treatment of DH (see Section 3.2).

Practitioners will be asked about their patients' predisposing and enabling variables at/ or soon after the baseline visit (see Section 3.2.2).

At the baseline visit after the oral examination, patients will complete a pain assessment questionnaire that will ascertain the pain intensity, frequency, and duration. Patients will record pain levels by using LM pain scales that were developed at the University of Washington specifically to assess the pain associated with DH (Heaton et al., 2013). These four 100-millimeter (mm) horizontal scales are labeled with descriptive terms to assess the intensity, duration, tolerability and description of the participant's pain experience. Patients will also complete a standard 100-mm horizontal VAS on which the endpoints are marked "not painful" and "most intense pain sensation imaginable."

The clinical symptom of DH is likely associated with the "overall patient experience" because there is likely spatial summation. When an individual drinks cold fluids, for example, his/her DH/pain would be associated with multiple teeth (if multiple teeth are sensitive). Rating each tooth could only be achieved if the dentist systematically isolated each tooth and stimulated each one separately -- which doesn't mimic the clinical condition. The VAS/LM ratings will be applied to assess the overall patient pain experience associated with DH. The LM pain scales capture specific dimensions of pain that characterize the DH pain response (Heaton et al., 2013).

At 1-, 4- and 8- weeks post-baseline and/or second/third-line treatment visit(s), pain intensity, frequency, and duration will be re-ascertained as described above to measure patient-reported pain outcomes via an online or mailed questionnaire. Compliance with treatment will also be assessed via one Likert-like question. Treatment satisfaction will be assessed by one VAS question 8-weeks post the last treatment visit.

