Analysis approach: Occurrence of patient-reported symptoms, predisposing factors and other patient-level variables, and practitioner-reported restoration-level and practice-level variables will be compared among the treatment modalities using a mixed-model multiple logistic regression approach. A term representing the individual practitioner will be specified as a random effect in the analytic model, and GEE estimation will be utilized in order to account for the clustering effect of multiple patients for each practitioner. Analyses will be conducted using each of the treatment modalities as the dependent variable. Potential predictor variables will be evaluated for association with the use of each treatment modality.

#2. To characterize patients' satisfaction with the received treatment of DH.

Analysis approach: Patients' reported satisfaction scores will be compared among the treatment modalities using mixed-model analysis of variance (ANOVA), accounting for correlated observations within practitioner. The specific implementation of the mixed-model ANOVA, as a normal-theory general linear model or a generalized linear model for non-normal data, will be based on the sample distribution of the scale scores. The statistical test that will be of primary interest will be the test for a main effect of treatment modality. Multiple comparisons will be conducted using Tukey's adjustment for multiple comparisons.

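### A treatment replaced within 8 weeks normally gets no satisfaction rating, so the comparison of satisfaction among modalities is informatively incomplete

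*Protocol*

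**What the plan says.** Protocol Section 3.2.2 gives two rules. In general, "patients' satisfaction with the prescribed treatment modality will be assessed via VAS at 8 weeks post-baseline". For patients who go on to a second or third line, "the VAS assessment will be implemented at 8 weeks after the initiation of the last line of treatment". Section 7.2 repeats the second rule: "Treatment satisfaction will be assessed by one VAS question 8-weeks post the last treatment visit". Section 4 adds that, once a further line begins, "follow-up assessments from the previously administered or prescribed treatment will no longer be warranted". Appendix A agrees: satisfaction is marked at the 8-week follow-up of each line and at an in-office withdrawal, but not at the second- or third-line visit, although pain is reassessed there.

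On who receives a further line, Section 4 says: "Patients who do not have a reduction of symptoms after the first-line treatment may return to the participating dentist". Section 6.6 adds the dentist's recommendation, "if the dentist routinely utilizes a" stepped approach.

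Section 11.2 (Secondary Objective #2) compares satisfaction scores among modalities by mixed-model ANOVA: "The statistical test that will be of primary interest will be the test for a main effect of treatment modality". It states no term for line of treatment and no caveat about replaced treatments.

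**The concern.** Whether a first treatment is rated depends on what happened after it was given. Patients who move on tend to be those it did not help, or those whose dentist works in steps. Their opinion of the replaced treatment is normally not asked for, and their only score goes to a later modality. If modalities differ in how often their failures are replaced, the observed means differ from the means over all patients who received them, and by different amounts. A modality often used as a later line is also rated by patients who have already left another treatment.

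At stake is the interpretation of the main test for a stated secondary objective. This is a data-collection rule, so no statistical analysis plan can recover a rating that was never requested.

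**Working it through.** **Step 1: which first treatments are rated.** The week-8 questionnaire is due on day 56 ± 6 (Section 6.5), so its window is day 50 to day 62. A second-line visit may fall on days 1 to 56 (Section 6.6.1).

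- No further line: the first treatment is rated at week 8, whether it worked or not.
- Second line on days 1–49: the visit comes before the rating window opens, and the rating is then dropped.
- Second line on days 50–56: a rating may already have been returned.
- In-office withdrawal without withdrawal of consent: satisfaction is collected (Section 6.7).

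The same pattern applies to a second line replaced by a third.

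**Step 2: number of ratings involved.** The planned total reproduces: 180 × 14 = 2,520 (Section 11.1). The protocol states no share of patients with further lines and no precision for satisfaction. For assumed shares of 5%, 10%, 20% and 30%, first treatments left unrated would number up to 2,520 × share = 126, 252, 504 and 756.

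**Step 3: effect on a comparison of first-line ratings.** All inputs here are assumed. Mean satisfaction is 80 after a first-line success and 40 after a failure. Modality A succeeds in 70% of patients and B in 50%. A share r of failures is replaced unrated, the same in both. With success probability p,

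observed mean = [80p + 40(1 − p)(1 − r)] / [p + (1 − p)(1 − r)].

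The true means are 0.7 × 80 + 0.3 × 40 = 68 and 0.5 × 80 + 0.5 × 40 = 60, a difference of 8. For r = 50%, A is (56 + 6)/0.85 = 72.9 and B is (40 + 10)/0.75 = 66.7.

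| r | Unrated, A / B | Observed mean, A / B | Difference | Shrinkage |
|---|---|---|---|---|
| 0% | 0% / 0% | 68.0 / 60.0 | 8.0 | 0% |
| 10% | 3% / 5% | 68.9 / 61.1 | 7.8 | 2% |
| 25% | 7.5% / 12.5% | 70.3 / 62.9 | 7.4 | 7% |
| 50% | 15% / 25% | 72.9 / 66.7 | 6.3 | 22% |
| 75% | 22.5% / 37.5% | 76.1 / 72.0 | 4.1 | 48% |
| 100% | 30% / 50% | 80.0 / 80.0 | 0.0 | 100% |

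With success of 80% against 40%, the shrinkage is 2%, 21% and 100% at r = 10%, 50% and 100%.

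**Step 4: replacement rates that differ by modality.** Take two modalities that both succeed in 50% of patients, so both have a true mean of 60. If 10% of one's failures are replaced, its observed mean is (40 + 18)/0.95 = 61.1. If 50% of the other's are, its mean is (40 + 10)/0.75 = 66.7. The gap is 66.7 − 61.1 = 5.6 points with no true difference, in favour of the modality whose failures are replaced more often.

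The model covers first-line ratings only. It treats every replacement as a failure, which overstates selection on outcome where a further line follows a routine stepped approach.

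**The case against.** The best defence is that the objective is to characterise satisfaction with the treatment received, in a study described as driven by estimation. Satisfaction 8 weeks after the final treatment is a coherent target for usual care. First-line failure is not lost either, because the pain scales are repeated at the return visit. Section 11.2 names a family of models without excluding a term for line, and a statistical analysis plan may add one; treatment is recorded at every line. All of this stands. It supports a conclusion about the final treatment received, but not an unqualified ranking of modalities. A line term would separate first- from later-line ratings without supplying the missing ones.

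Four stronger readings are tempting and are not supported:

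- A reader might infer that patients whose first treatment failed never rate it. Return is optional, and those given no further line rate it at week 8. A rating on days 50–56 or at an in-office withdrawal is also possible.
- A reader might infer that the ratings are selected on success. They are selected on not being followed by another line, which also reflects practice style. Patients whose last line failed rate that line.
- A reader might infer a bias in favour of first-line treatments as a class. Nothing in the protocol fixes that direction; what follows is an advantage for modalities whose failures are replaced more often.
- A reader might infer that a difference of about 7 mm would disappear. Such a case can be built: with ratings of 75 mm from patients who stay and 30 mm from those who return, and 20% against 5% returning, the true means are 0.8 × 75 + 0.2 × 30 = 66 and 0.95 × 75 + 0.05 × 30 = 72.75, while both are observed as 75. None of these inputs is in the protocol, and the example requires that patients who stay give the same mean rating under both modalities.

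**Conclusion.** The point holds in a limited form. Patients who receive a second or third line within 8 weeks normally give no satisfaction rating of the treatment that was replaced, and the reasons for a further line are partly related to outcome. Ratings of replaced treatments are therefore informatively incomplete, and the planned modality test tends to flatter modalities whose failures are more often replaced.

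The size cannot be derived from the protocol. On the assumed two-class model it is slight when few failures are replaced (about 2% shrinkage at 10%), moderate at half (about 22%), and complete only if every failure is replaced. It could also create an apparent difference where replacement rates differ between modalities. This concerns a secondary, descriptive outcome; it leaves the sample size and the primary objective untouched. It is a worthwhile and inexpensive improvement.

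**What to change.** Add the satisfaction VAS, worded for the current treatment, to the pain assessment already done at the second- and third-line visits, and state that it is completed before the new treatment. In the Section 11.2 model, analyse scores by the modality rated, with line of treatment as a term. Keep the 8-week rating as the measure of satisfaction with the final treatment. Report an additional analysis that includes the ratings of replaced treatments, noting that they are taken earlier than 8 weeks (from day 1 onwards) and in the office instead of by remote questionnaire. For that reason they should not be pooled with the week-8 ratings as the main comparison.

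If the item is not added, limit the conclusion to satisfaction with the final treatment received, and report by modality how many patients went on to another line.

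The cost is one item at visits that already take place, one model term, and an amendment to the form, which needs review by the six or more boards mentioned in Section 14.2. The protocol already accepts an off-schedule satisfaction rating at in-office withdrawal, so there is a precedent for collecting one when a patient leaves a treatment.
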